Figure 1. The direct nephrotoxicity of contrast agents has decreased while exposures have dramatically increased. Contrast-enhanced CT imaging, particularly from the emergency care setting, is now the major source of patient exposures to contrast media agents.

Despite a lack of definitive evidence, significant effort and costs are associated with both the prevention and treatment of CIN. Precedent literature attributes CIN with marked increases in hospital mortality, prolonged hospitalization and increased costs.^{1,33,34} Over one quarter of all laboratory testing in the emergency care setting alone is performed with the express purpose of identifying patients at increased risk of CIN.³⁵ National and international cardiology and radiology organizations continue to invest resources into developing and promoting national guidelines aimed at reducing CIN.³⁶⁻⁴² However, research aimed at quantifying the potential impact of reducing contrast media exposure is limited to a single active meta-analysis protocol.³⁰ There are no active, randomized trials that address this long-standing controversy. (www.clinicaltrials.gov, accessed 3/10/2015).

The following conditions are necessary for a trial of this type:

- 1) Prospective Design: With CIN, the characteristic rise in creatinine does not peak for 3 to 5 days, or longer in more severe cases.^{43,44} Similarly, the change in creatinine needed to identify other causes of AKI is variable. Moreover, routine, compulsory post-exposure surveillance for AKI is not currently the standard of care, or even common practice, especially in the outpatient and reduced-hospital stay settings. As such, retrospective, post-exposure data are likely to severely and unpredictably underestimate both the relative contribution of CIN and other causes of AKI.^{14,16,32,45}
- 2) Controlled, Randomized Exposure: Contrast media is administered for specific clinical indications; populations undergoing contrast-enhanced and non-contrasted diagnostic studies are distinct, and differ significantly in terms of acute illness state and risk of CIN or other AKI. Thus, unstructured comparisons between these populations are severely limited.
- 3) Comparison of Clinically Equivalent Diagnostic Imaging Tests: The standard contrast-enhanced study(ies) and the non-contrast alternative(s) must have equivalent diagnostic accuracy and cannot carry significantly higher risk of adverse events (e.g. radiation exposure, invasiveness, etc.).

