The 45-day incidence of VTE in patients with a calculated pre-test risk between 2.5% and 20% was 3%. Importantly, the accepted test threshold prompting imaging for suspected PE is very low: only 2.5%.^{13,48} As such, <15% of patients who underwent imaging for suspected PE ultimately were ultimately diagnosed with VTE. Pre and post-CTPA creatinine data were available for 30% of a validation subset (834 patients from 4 institutions)

[figure not shown]

Figure 3. Example output of the PE PreTest Consult Score (<http://pretestconsult.com/v21/pe>), which allows clinicians to calculate the point-estimate of an individual patient's pre-test probability of pulmonary embolism, at the bedside, using an attribute matching method leveraging over 2 decades of data, from over 8,000 patients evaluated at 7 medical centers, developed by a co-investigator ([name]) along with the PI.^{47,56-59}

[figure not shown]

Figure 2. Cumulative hazard plot for 1-year mortality for patients with and without Contrast-Induced Nephropathy (CIN), adjusted for age and the presence of an active malignancy at the time of enrolment. ($p < 0.01$).

evaluated simultaneously for both suspicion of acute coronary syndromes and PE. In patients at low and moderate risk of PE (pre-test VTE risk $\leq 20\%$), the rate of AKI consistent with CIN, did not differ with the presence (9%) or absence (8%) of a VTE.

The PI has developed methods of risk-stratifying patients for CIN in the emergency care setting: Using data from her contrast-enhanced CT cohort of patients treated in the emergency care setting, the PI evaluated over 100 literature derived risk factors (at varying thresholds) for CIN^{18,23,28,41,60-83} and derived the AKIrisk Score: 2 points for glycosuria on urine dipstick; and 1 point each for Age ≥ 50 years, measured diastolic blood pressure ≥ 100 mmHg, history of HIV or AIDS, and a history of coronary artery disease.⁸ Importantly, an elevated creatinine (SCr), corresponding to an estimated glomerular filtrate rate (eGFR_{SCr}) ≤ 60 ml/min/m²,¹⁷ did not accurately risk-stratify patients for CIN: sensitivity 13%, area under the receiver operating characteristic curve (AUROC) 0.55.^{9,10} In comparison, a AKIrisk Score of ≥ 2 points more accurately predicted CIN: sensitivity 56% (95% CI 43 to 68%), specificity 81% (95% CI 77 to 84%), AUROC of 0.74 (95% CI 0.68 to 0.81) and positive predictive value (27%, 95% CI 20 to 34%).⁸⁻¹⁰ (Figure 4)

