2.2 Secondary objectives

The secondary objectives of this study are to:

- 1) Validate the AKIRisk score, alone and in combination with acute-phase markers of renal dysfunction (Cystatin-C and/or NGAL), to inform imaging strategies and reduce the risk of AKI.
- 2) Compare the incidence of short, mid- and long-term AKI and subsequent health outcomes in patients exposed to iodinated contrast media and unexposed controls at 30-days and at 1-year.
- 3) Measure the 30-day and 1-year incidence of VTE and subsequent severe health outcomes including outcomes related to VTE and VTE treatment.

All secondary outcomes will be defined using composite outcomes and will be determined to be present or absent by the agreement of 2 of 3 blinded physician reviewers, using methods of adjudication successfully employed by the PI in comparable studies.^{7,11,20,46,53,59} Briefly, physician reviewers will be provided with copies of the EMR and patient interview responses. Identifying information will be redacted, and, while the reviewer will have access to any creatinine values recorded in the EMR, they will not be provided with creatinine measurements performed for the study and not recorded in the EMR, nor will they be informed of the subject's status with regard to the primary outcome. Each reviewer will be asked to define each secondary outcome as present or absent, without knowledge of the other reviewers' determinations. In the event of a disagreement between the first and second reviewer, the determination of a third reviewer will be used to define the outcome. No reviewer will be made aware of their designation as the first, second or third reviewer.

Acute Kidney injury will be reported using defined using the Acute Kidney Injury Network (AKIN) definitions (stages 1-3).⁹⁰ KDIGO guidelines do recommends a more standard definition of AKI than for CIN.³⁸ While we do agree with this recommendation, in principle, we are planning a study aimed at changing imaging practices of physicians in specialties that are not as familiar with the. We do plan to measure and report AKIN 1-3 outcomes. We also plan the enrollment of a heterogeneous cohort of patients with renal function ranging from normal to significantly impaired and patients with a range of acute and chronic illnesses of varying severity, consistent with patients treated in the emergency care setting.

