3.3 Duration of Subject Participation

Patient involvement will last one year, inclusive of follow-up review of their medical records. The primary outcome of AKI consistent with CIN will be measured once between 2 and 7 days (≥ 48 hours and ≤ 168 hours) after enrollment PE imaging. Safety outcomes will be followed for occurrences up to 7 days after the enrollment PE imaging study. Secondary study outcomes will be assessed starting at 30-days and 1-year.

4. Study Population

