5.1 Main Measurements

Collection of blood and urine samples may be obtained around enrollment and the initial follow-up (2-7-days). We will collect blood and urine samples, using standard collection methods.

Enrollment Data Collection: The study coordinator will collect the following data: age; sex; race and ethnicity; vital signs; current medications and treatments (including anticoagulation and/or thrombolysis treatment for VTE); comorbid conditions (acute and chronic); the type and severity of prior adverse reactions to iodinated contrast media; physiologic indicators of acute disease (EKG findings of cor pulmonale, indications of right-heart strain and other echocardiography data, cardiac biomarkers including troponin and brain natriuretic peptide [BNP], and lactate); and literature-derived risk factors for CIN.^{18,23,28,41,60-83} We will also record the type and volume of intravenous fluid administered 12 hours prior to and within 24 hours following the enrollment imaging study.

Baseline Creatinine Measurement If the study participant received a baseline creatinine measurement, documented in the EMR, within 24 hours of imaging around enrollment, this measurement will be used as the baseline measurement for our study. If not, we will measure a creatinine level from the blood sample collected at enrollment, if applicable.

Follow-up Creatinine Measurement The follow-up blood draw and creatinine measurement will be performed no sooner than 48 hours and no longer than 7 days (168 hours) following the enrollment imaging study using methodology established by the applicant.^{7,11,20,89} At the time of enrollment, regardless of plans for discharge or

hospitalization, study participants will be scheduled for a return visit to their site of enrollment. The patient will receive a reminder card with the date, time, and location of their follow-up appointment and a contact phone number for the study coordinator. If the patient remains hospitalized 48 hours or more following the enrollment imaging study, we will record the highest creatinine value measured during the specified follow-up time of 2-7 days, or if needed, complete the creatinine measurement. If the patient is hospitalized, but discharged prior to the follow-up period, follow-up will be completed as previously scheduled. A \$50 dollar stipend will be provided for patients that complete the return appointment as reimbursement for travel costs and time.

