5.3 Study schedule and benchmarks

Study Events Schedule						
Procedure	Screening/ Enrollment	24 Hours after PE Imaging	≥ 48 hours and ≤168 hours	7-Day Follow-up	30-Day Follow-up	1-Year Follow-Up

			after PE imaging			
Inclusion/Exclusion Review	X					
Informed Consent	X					
Chest Radiograph	X		X			
Urine Sample	X		X			
Blood Sample/Creatinine	X		X			
Interview			X	X (If return visit not completed)		
EMR Review	X	X	X	X	X	X
Assess Primary Outcome			X	X		
Assess Secondary Outcomes		X	X	X	X	X
Asses SAEs		X	X	X		

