6.0 Safety Assessment and Reporting

The study coordinators will also communicate closely with the clinical team, inform them of the PE imaging randomization assignment, and assist the clinical team to coordinate the completion of the PE imaging. The study coordinator will notify the treating provider of any conditions that exclude the patient from participation in this study. A study physician will be available by telephone during patient enrollment and the completion of PE imaging. The flowchart shown in appendix 1. describes the study procedures including randomization, assessment of outcomes, and PE imaging completion, including the process for crossover from the VQ arm to CTPA. Patients with suspected DVT will also undergo lower extremity ultrasound (US), at the discretion of the treating provider, as will patients with an intermediate risk VQ. Thus, only patients who, after pre-enrollment screening for non-high risk of PE, appropriateness for VQ imaging, have an intermediate risk VQ study and a negative DVT US, will require crossover to CTPA to exclude PE.

Patients who develop CIN, based on the study definition and follow-up creatinine measurement, will receive a telephone call notifying them of this result. If the patient cannot be reached by telephone, we will also send a letter (paper mail, and if provided, email) informing them of their creatinine measurement. The same notification letter will provide instructions to seek follow-up care with either their primary care physician, or for patients without a primary care physician, with instructions to follow-up in the emergency department.

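### Late AKI is to be compared between arms, but no study creatinine is taken after day 7 and adjudication has no 'not measured' option

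*Combined protocol and SAP*

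**What the plan says.** **Objective.** Section 2.2 lists as secondary objective 2: "Compare the incidence of short, mid- and long-term AKI and subsequent health outcomes", in patients exposed to contrast and in unexposed controls, at 30 days and 1 year. The same section says AKI will be reported by AKIN stages 1-3. On timing, section 3.3 states: "Secondary study outcomes will be assessed starting at 30-days and 1-year".

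**Measurement.** Section 5.1 fixes the only post-imaging study creatinine: "The follow-up blood draw and creatinine measurement will be performed no sooner than 48 hours and no longer than 7 days (168 hours"). Section 1.6 allows for at most two blood draws. In the section 5.3 schedule, the row "Blood Sample/Creatinine" is marked at enrolment and at 48-168 hours. It is blank at 30 days and 1 year, where only record review and outcome assessment are marked.

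**Late sources.** Section 5.1 takes 30-day and 1-year outcomes from the medical record. For renal failure (AKIN 3), section 2.2 uses the highest creatinine in the record during the period, or the need for renal replacement therapy.

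**Adjudication.** "Each reviewer will be asked to define each secondary outcome as present or absent". Section 2.2 gives no option for an outcome that could not be assessed. Reviewers see creatinines in the medical record but not study values that were never entered there.

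**Notification.** Section 6.0 has patients who meet the study definition of CIN telephoned with the result. A letter follows if they cannot be reached: "The same notification letter will provide instructions to seek follow-up care".

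**The concern.** AKIN 1 and 2 are creatinine diagnoses and, as section 2.1 acknowledges for the first stages of AKI, usually silent. Without a scheduled sample they are found only when someone has another reason to test. The protocol knows this: section 1.4 observes that "routine, compulsory post-exposure surveillance for AKI is not currently the standard of care", and uses the point to argue for a prospective design.

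Two consequences follow. First, the recorded incidence of late AKI is the true incidence multiplied by some unknown chance of being tested. Second, that chance may differ by arm. Patients who meet the primary outcome are told so and may have more creatinines ordered afterwards. If contrast raises early AKI, the CTPA arm would then be tested more in the following weeks and months, and extra late AKI in that arm could reflect testing rather than lasting injury. Randomisation does not protect against detection that depends on a result obtained after randomisation.

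**Working it through.** **Step 1. Can late AKIN 1-2 be seen without a clinical test?** Sections 5.1 and 5.3 provide no study sample after 168 hours, and the late source is the medical record. The interview row of the schedule is marked only at 48-168 hours, and at day 7 when the return visit was missed. So AKIN 1-2 after day 7 needs a clinically ordered creatinine. AKIN 3 can also be reached through renal replacement therapy.

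**Step 2. What happens to an untested patient?** The reviewer must choose present or absent. With no creatinine and no dialysis, absent is the natural choice. This is an inference: the plan does not state it. The multiple imputation in section 2.1 is conditional and applies to missing values. A patient adjudicated as absent is not missing, so it would not be triggered.

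**Step 3. Under-count.** The plan gives no figure to reproduce: neither a late testing share nor a late AKI rate. If testing were unrelated to outcome,

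recorded rate = true rate × share tested.

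A true 10% would be recorded as 7%, 5% or 3% with 70%, 50% or 30% tested. The lowest share is prompted by section 1.5: "Pre and post-CTPA creatinine data were available for 30% of a validation subset". That figure describes paired values in another cohort with no stated window, so it serves only as one end of a range.

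**Step 4. Differential testing.** Let p be the early AKI rate in an arm, t the share of notified patients retested and r the routine testing share among the rest:

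share tested = p·t + (1 − p)·r.

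If true late AKI risk is equal in both arms and unrelated to testing, the spurious rate ratio is the ratio of the tested shares. Inputs:

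- t = 0.80 (assumption).
- r = 0.30 to 0.70 (assumption).
- Early AKI 20% vs 10%: a 10-point difference, as in the sample-size text of section 2.1; the rates themselves are illustrative.
- Early AKI 32% vs 6%: Table 3 in section 1.5.

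| Routine testing r | 20% vs 10%: tested | Ratio | 32% vs 6%: tested | Ratio |
|---|---|---|---|---|
| 0.30 | 0.16 + 0.24 = 0.40 vs 0.08 + 0.27 = 0.35 | 1.14 | 0.256 + 0.204 = 0.46 vs 0.048 + 0.282 = 0.33 | 1.39 |
| 0.50 | 0.16 + 0.40 = 0.56 vs 0.08 + 0.45 = 0.53 | 1.06 | 0.256 + 0.34 = 0.596 vs 0.048 + 0.47 = 0.518 | 1.15 |
| 0.70 | 0.16 + 0.56 = 0.72 vs 0.08 + 0.63 = 0.71 | 1.01 | 0.256 + 0.476 = 0.732 vs 0.048 + 0.658 = 0.706 | 1.04 |

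At r = 0.30, moving t from 0.60 to 1.00 gives 1.09-1.19 for the first pair (0.36/0.33 to 0.44/0.37) and 1.25-1.53 for the second (0.396/0.318 to 0.524/0.342). If p is the same in both arms, the ratio is 1 whatever t and r are.

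**Step 5. Absolute size.** At a true late rate of 10% and r = 0.30, the recorded rates are 4.0% vs 3.5%, or 4.6% vs 3.3%. With 300 per arm and a two-sided 5% test (normal approximation), these false differences would be declared significant about 6% and 13% of the time.

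**The case against.** **The late endpoints may be narrower than the objective's wording.** The synopsis lists mid- and long-term endpoints as severe health outcomes. Section 2.2 defines these as death, renal failure (AKIN 3), myocardial infarction, stroke and other arterial events, and the secondary analysis text gives similar examples. The only explicit window for AKIN 1-3 is 168 hours, in the safety endpoint. The synopsis version of objective 2 could mean early AKI followed by later outcomes. This has force, and it means that much of the remedy is already in the plan. But section 2.2 names mid- and long-term AKI outright, so the two texts need to be brought into line.

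**Several stronger readings are tempting, and the documents do not support them.**

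- A reader might infer that untested patients can only be scored absent, or that the objective cannot be met at all. Renal replacement therapy counts without a creatinine, and clinically recognised AKI can still be compared.
- A reader might take section 1.4 as condemning any unscheduled creatinine data. Its warning about severe underestimation concerns retrospective data, in a passage on the delayed creatinine peak. The parallel is fair, but it is only a parallel.
- A reader might think every patient with early AKI is instructed to seek care. Section 6.0 plans to notify each patient with CIN. It describes the care instructions only in the letter for those not reached by telephone.
- A reader might treat 30% as the expected late testing share. The randomised patients all have AKIrisk Score ≥2, and section 4.1 reports many comorbidities and about 65% admitted, so routine testing could be much higher. The table shows how quickly the bias shrinks as it rises.

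**The under-count may be milder than Step 3 suggests.** Clinicians test sicker patients, so fewer cases would be lost than when testing is unrelated to outcome. That stands, and it is why no single figure is offered.

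**Conclusion.** The point holds as a mismatch between a stated comparison and the data collected for it. Late AKIN 1-2 depends on clinically ordered tests, and the adjudication rule would in effect turn untested patients into non-events. Under-counting follows from the design, though its extent is unknown.

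Bias between arms is possible rather than established. It needs a real difference in early AKI and more retesting of notified patients than of others. Under the trial's own hypothesis of no contrast effect, this route to bias closes. On the stated assumptions (80% retesting, equal late risk unrelated to testing, routine testing of 70% down to 30%), the spurious ratio is about 1.01-1.14 for early AKI of 20% vs 10%, and 1.04-1.39 for 32% vs 6%. The second pair comes from a retrospective matched sample that included patients with AKIrisk Score <2, so it is an outer case. These figures illustrate direction and scale; they are not forecasts.

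The primary endpoint, which uses the 48-168 hour creatinine, is unaffected.

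**What to change.** 1. In the synopsis and section 2.2, limit the inferential between-arm comparison of AKIN 1-3 to the 48-168 hour window. State that it uses the study creatinine. As written, reviewers are not shown study values missing from the medical record, so even the day 2-7 AKIN outcome could miss cases found only by the study draw.
2. At 30 days and 1 year, compare the severe health outcomes that section 2.2 already defines. Keep renal failure as defined there, but label it as clinically detected.
3. Add 'not measured' to the adjudication options for creatinine-based outcomes, so that untested patients are not counted as event-free.
4. Report AKI after day 7 from the medical record descriptively, with the share of patients tested shown by arm.

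The cost is a change of wording and one extra adjudication category, with no added visit or blood draw. The downside is a narrower claim for one secondary objective. AKI found after day 7 remains a description of tested patients, since who is tested may itself differ by arm.

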Venous Thromboembolism (VTE) including PE and/or DVT will be defined by the identification of one or more thrombus, requiring medical or surgical intervention, in the deep veins of the extremities or in the pulmonary vasculature as determined by ultrasonography, echocardiography, CT, MRI, VQ or on autopsy. We will also record and report severe outcomes secondary to VTE and treatment of VTE, including hemorrhage from anticoagulant treatment.

Complications of PE imaging will be defined for the first 24 hours after imaging, patients will be followed for one or more of the following recorded in the EMR, and requiring medical or surgical intervention: hypotension defined as a SBP ≤90 mmHg or ≥10% below baseline, dyspnea, acute pulmonary edema or hypervolemia, oral swelling, rash or puritis, abdominal pain, nausea or vomiting, altered mental status, or soft tissue contrast media or radio-isotope extravasation. The PI has previously published these methods of outcome determination.⁵³

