Severe Health Outcomes will be defined for each follow-up period (24 hours, 2-7 days, 30 days, and 1 year) as the combined outcome of death from any cause, renal failure, acute myocardial infarction, stroke, and/or one or more symptomatic complications of arterial-vascular disease, in any distribution, (cerebral, coronary, mesenteric, renal or peripheral) requiring surgical or medical therapy.²⁸ Renal failure will be defined by the AKIN 3 criteria: an increase in creatinine 3 times baseline, or a decrease in eGFR_{Scr} $\geq 75\%$, or an absolute increase in creatinine to ≥ 4.0 mg/dL as a result of an increase of at least 0.5 mg/dL, or the need for renal replacement therapy.⁹⁰ The highest recorded creatinine recorded in the EMR during the follow-up period will be used to determine this outcome. Myocardial infarction will be defined as a cardiac catheterization, autopsy or cardiac imaging study demonstrating acute coronary thrombus or non-viable myocardium; or at least one measured troponin I above the 99th percentile and clinical findings consistent with ischemia; or diagnostic ECG findings including acute ST-T changes, new left bundle branch block, or new pathologic Q-waves.^{96,97} Stroke will be defined as an acute, focal neurologic deficit with symptoms lasting longer than 24 hours and/or imaging or autopsy evidence of acute cerebral infarction. Finally, coronary or cerebrovascular events not meeting the criteria for acute myocardial infarction or stroke, including acute coronary syndromes and transient ischemic attack (TIA), are included within the definition of other arterial vascular events if these events required medical or surgical invention. The PI has successfully applied the same methods of outcome determination in a comparable study.^{7,11,20}

Outcomes involving death will be classified by adjudicators as: 1) Renal injury as a significant contributor defined as obvious evidence of renal failure defined by worsening azotemia with complications of renal failure including oliguria, pulmonary edema, hyperkalemia, pericardial effusion, or the need to initiate renal replacement therapy before death; 2) Death from VTE and/or hemorrhage requiring intervention following anticoagulant treatment for VTE; or 3) Unrelated to VTE or Renal injury. Death outcomes 1) and 2) may be identified concurrently.

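### Secondary-outcome reviewers are called blinded, but the plan hides neither the imaging arm nor the scan type from them

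*Combined protocol and SAP*

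**What the plan says.** Under Section 2.2 (Secondary objectives), every secondary outcome "will be determined to be present or absent by the agreement of 2 of 3 blinded physician reviewers". The packet and its redaction are described in these words: "physician reviewers will be provided with copies of the EMR and patient interview responses. Identifying information will be redacted". The section then lists what else reviewers do not get:

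- On laboratory data: "they will not be provided with creatinine measurements performed for the study and not recorded in the EMR". Creatinine values that are in the record remain available, and the section says so.
- Primary-outcome status, the other reviewers' determinations, and whether one is first, second or third reviewer.

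Some of the outcomes judged this way name the modality or the agent. VTE is established from imaging that includes CT and VQ. Complications of PE imaging end with "altered mental status, or soft tissue contrast media or radio-isotope extravasation". Others call for interpretation. Deaths are classified by adjudicators, the first category being "Renal injury as a significant contributor defined as obvious evidence of renal failure defined by worsening azotemia". Myocardial infarction can rest on a raised troponin plus clinical findings of ischemia.

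**The concern.** The imaging test is not concealed from anyone at the bedside. Section 6.0 has the coordinator tell the clinical team the assignment and help arrange the scan. Masked adjudication is therefore an important safeguard for the between-arm comparisons of judgement-dependent outcomes, alongside explicit definitions and independent review. Calling the reviewers blinded invites readers to assume they do not know the arm. If the packet is prepared as described, nothing ensures that. A reviewer who knows whether the patient received contrast may settle borderline cases differently in the two arms. Two reviewers sharing the same expectation would agree with each other, so the agreement rule would not remove the error.

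**Working it through.** The plan states no figure on this point, so the main check sets the sections against each other.

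**Is the arm hidden anywhere?**
- Section 2.2: the hidden items are those listed above. Arm, modality and agent are absent.
- Section 1.6 (Known Potential Risks): redaction means removal of protected health information.
- Section 6.3 (DSMB charter, item 5): masking to assignment is mentioned, but only as a choice for the board.
- I found no other text that masks the reviewers to arm.

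**Would the packet reveal it?**
- The index-visit record would ordinarily hold the scan order, the report and the administration of contrast or isotope.
- Patients know which scan they had, and no rule strips this from interview answers.
- Section 1.6 allows non-contrast CT or SPECT in the VQ arm, and Section 6.0 adds ultrasound after an intermediate VQ. The second clue is weaker, since suspected DVT also leads to ultrasound.
- Section 2.1 expects crossover from VQ to CTPA below 5%, so the scan seen is close to a direct label of the arm.

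**Which outcomes depend on judgement?**

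| Outcome (Section 2.2) | Room for arm-dependent judgement |
|---|---|
| Renal or VTE contribution to death | Yes |
| Myocardial infarction on clinical findings; other vascular events | Yes |
| Whether an event required intervention | Yes |
| All-cause death | Little |
| Renal failure (AKIN 3: creatinine, eGFR or renal replacement) | Little |
| Primary endpoint (creatinine change, Section 2.1) | None from this process |

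Because the Severe Health Outcomes composite counts death from any cause, classifying the cause cannot change that composite.

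**Illustration of size.** Inputs from Section 2.1: n = 300 per arm and a two-sided 5% level. Assumed, because the documents give neither: a true event rate p, equal in both arms, and a fraction f of event-free patients whom the panel wrongly calls positive in one arm only.

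- Apparent rates: p1 = p + (1 − p)f and p2 = p, so d = (1 − p)f.
- SE0 = √[2p̄(1 − p̄)/n], where p̄ = (p1 + p2)/2.
- SE1 = √{[p1(1 − p1) + p2(1 − p2)]/n}.
- Rejection probability = 1 − Φ[(1.96·SE0 − d)/SE1] + Φ[(−1.96·SE0 − d)/SE1].

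For p = 0.05 and f = 0.02: p1 = 0.069, d = 0.019, p̄ = 0.0595, SE0 = 0.01932 and SE1 = 0.01930. The two terms are 1 − Φ(0.977) = 0.164 and Φ(−2.946) = 0.002, which sum to 0.166. The bias amounts to 300 × 0.019 = 5.7 extra events.

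| f | p = 5% | p = 10% | p = 15% |
|---|---|---|---|
| 0 | 5.0% | 5.0% | 5.0% |
| 1% | 8.0% | 6.5% | 6.0% |
| 2% | 16.6% | 10.9% | 8.8% |
| 5% | 60.5% | 39.0% | 28.2% |

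With 200 per arm and f = 2%, the values are 12.6%, 8.9% and 7.5%. This is an unadjusted two-proportion test. The plan's covariate-adjusted logistic regression would give somewhat different numbers.

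**The case against.** The strongest reply is that the visibility of the arm is inferred. The protocol never says reviewers see it. Its account of adjudication is introduced as brief and refers to published methods that are not available here, and the word blinded may have been meant to cover arm. This stands as a limit on certainty. It does not supply a procedure, however. One of the comparable studies, the contrast-enhanced CT cohort in Section 1.5, had no randomised arm to mask, so precedent does not settle the matter.

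Other safeguards also exist: explicit criteria, independent determinations, a third reviewer for disagreements and concealed reviewer order. These reduce the room for bias. None of them hides the arm.

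Several stronger readings are tempting, and the documents do not support them:

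- *Errors would favour finding harm from CTPA.* Section 1.2 hypothesises that avoiding contrast does not change AKI risk, while the preliminary data in Section 1.5 point towards harm. The direction cannot be predicted.
- *Reviewers must decide whether a symptom was caused by the scan.* Section 2.2 asks only whether listed events were recorded within 24 hours and required intervention, and it gives a numeric threshold for hypotension.
- *The 7-day safety comparison depends on this panel.* Section 5.2 gives that monitoring to the study manager and mentions no panel.
- *Primary-outcome status is covertly exposed.* For patients still in hospital at 48 hours, Section 5.1 draws the endpoint from values that may be in the record. Section 2.2 openly states that reviewers see recorded creatinine.

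**Conclusion.** The point holds for secondary outcomes that require judgement. As written, the plan describes blinded review without hiding arm, modality or agent, and the packet would ordinarily disclose them. Misclassification could go in either direction. The primary endpoint is untouched, and all-cause death and AKIN 3 renal failure are little affected.

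The size is unknown. The illustration shows that a one-arm false-positive rate of 2% would roughly double or triple the nominal 5% error rate at true event rates of 5% to 10%, and a rate of 1% would have a smaller effect. It rests on assumed rates and on error in one arm only, so it shows sensitivity and does not forecast bias.

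A reader might infer that reviewers are known to be unblinded, or that every secondary comparison is compromised. The text supports neither. It supports the narrower statement that no masking to arm is specified where it is needed and largely feasible.

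**What to change.** In Section 2.2 and the adjudication instructions:

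1. State that reviewers are blinded to randomised arm.
2. Extend the existing redaction, for both the record and the interview answers, to the index scan type, its orders and reports, contrast or radioisotope administration and, where feasible, follow-on imaging that reveals the arm.
3. Replace the index report with a neutral line stating whether PE was diagnosed, yes or no. Avoid a non-diagnostic category: the only indeterminate result the protocol describes is an intermediate VQ, so that label would point to the arm.
4. Have reviewers record cause of death, myocardial infarction, stroke and other vascular events on this packet before any unredacted imaging is released to confirm VTE.
5. Name the outcomes that cannot be fully masked: VTE, and extravasation of a named agent.

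The cost is more redaction time per packet, across up to 600 randomised records at five sites, and a second-step release for some VTE cases. Narrative notes will take the most effort and some clues will remain, hence the qualification about feasibility. Redaction of these packets is already planned, so this widens an existing step. Sample size, data collection and the primary analysis do not change.
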